
Safety All adverse events (AEs) will be analyzed in terms of descriptive statistics and qualitative analysis. Adverse events will be listed for each subject and summarized by system organ class and preferred term by using the Medical Dictionary for Regulatory Activities. Safety laboratory data, vital signs measurements and ECG data will be listed for each subject and presented descriptively by treatment group, visit and assessment time.

Data and Safety Monitoring: A Data and Safety Monitoring Board (DSMB) will be set up for the trial reviewing and evaluating unblinded safety data, and propose appropriate actions as necessary. An initial assessment of safety will be performed after the first approximately 12 subjects in the BEGEDINA arm have stopped study treatment.
 
Interim Analysis: In addition to the regular monitoring of safety, one interim analysis including certain efficacy data is planned when Day 28 response data is available for approximately 50% of the subjects. This analysis will be conducted by an independent, unblinded statistician and statistical programmer and results will be reviewed by the DSMB. Two objectives are associated with this interim analysis:
 
• a non-binding futility analysis that may lead to stop of the study if chances for a successful study outcome are too low• a submission of interim results to Health Authorities for conditional approval if interim results for overall response at Study Day 28 would be very convincing (i.e., with a one-sided p-value less than 0.001). Even in this case, the study will be continued as planned to determine the final results for response at Study Day 28, response and in particular the results for TRM, overall survival, other secondary efficacy endpoints and safety (all relevant for the assessment of unconditional approval).

Date of protocol: 13 March 2017

TABLE OF CONTENTS

1.0	LIST OF ABBREVIATIONS AND DEFINITIONS OF TERMS	14
2.0	INTRODUCTION.....	17
2.1	Background Information.....	17
2.1.1	Graft-Versus Host Disease	17
2.1.1.1	Acute Graft-Versus Host Disease.....	18
2.1.2	BEGEDINA®	19
2.1.2.1	Non-Clinical Pharmacology	20
2.1.2.2	Clinical Studies.....	24
2.1.3	Conventional Treatments for Graft-versus Host Disease.....	48
2.2	Rationale	48
2.3	Risk Assessment	49
3.0	STUDY OBJECTIVES.....	50
3.1	Primary Objective.....	50
3.1.1	Secondary Objectives: Efficacy	50
3.1.2	Secondary Objectives: Pharmacokinetic (PK)	50

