Table 10 Frequency of Responders at Day +28 (Dose-Finding Study, EudraCT No. 2012-001353-19)

	Treatment Group				Total (N=16)
	DL1 (N=3)	DL2 (N=3)	DL2bis (N=7)	DL3 (N=3)	
Responders at +Day 28, N (%)					
No ^a	1 (33.3%)	1 (33.3%)	2 (28.6%)	1 (33.3%)	5 (31.2%)
Yes	2 (66.7%)	2 (66.7%)	5 (71.4%)	2 (66.7%)	11 (68.8%)

^a Subjects who died before or at Day +28 were considered as not responders.

Source: Clinical study report Addendum1, Dose-finding study, EudraCT No. 2012-001353-19, Table 14.2.1.1.

Overall Survival at Day 180

Overall survival in the FAS is presented in Table 11. At Day +180, death had occurred in 6 out of 16 subjects (37.5%). By cohort, the deaths had occurred in all 3 subjects (100%) in the DL1 cohort, in 1 subject (33.3%) in the DL2 cohort, in 2 subjects (28.6%) in the DL2bis cohort, and in none of the subjects in the DL3 cohort.

The one-year overall survival was 56.2% (9/16 subjects).

Table 11 Overall Survival Day 180: Full Analysis Set (Dose-Finding Study, EudraCT No. 2012-001353-19)

	Treatment Group				Total (N=16)
	DL1 (N=3)	DL2 (N=3)	DL2bis (N=7)	DL3 (N=3)	
Death, n (%) ^a					
No	0 (0.0%)	2 (66.7%)	5 (71.4%)	3 (100.0%)	10 (62.5%)
Yes	3 (100.0%)	1 (33.3%)	2 (28.6%)	0 (0.0%)	6 (37.5%)
Overall survival (days) ^b					
n	3	1	2 ^c	0	6
Mean (standard deviation)	54.0 (31.5%)	24.0	66.5 (70.0%)	0	NC
Median	45.0	24.0	66.5	-	NC
Min, Max	28, 89	24, 24	17, 116	-	17, 116

^a Percentages are based on the number of subjects with data available in the FAS within each group

^b Overall survival was calculated on death

Source: Clinical study report Addendum1, Dose-finding study, EudraCT No. 2012-001353-19, Table 14.2.5.1.

[figure not shown]
Pharmacokinetic Results

DL1, DL2 and DL3 cohorts

Figure 2 shows the mean profile of BEGEDINA concentration in the 3 subjects in the DL1 cohort (dose 2 mg/m²), of the 3 subjects in the DL2 cohort (dose 3 mg/m²) and in the 3 subjects in the DL3 cohort (dose of 4.5 mg/m²), within 5 days of administration.

The PK results showed linearity in dose-concentration: highest mean BEGEDINA concentration was observed in subjects who received 4.5 mg/m² of drug (DL3 cohort), which was greater than the mean concentration in subjects who received 3 mg/m² of drug (DL2 cohort), which in turn was greater than mean concentration in those treated with the 2 mg/m² dose (DL1 cohort).

Figure 2 BEGEDINA Concentration Profile at Dose Levels 2 mg, 3 mg, and 4.5 mg/kg/day for 5 Days (Dose-Finding Study, EudraCT No. 2012-001353-19)

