All subjects in all dose cohorts reported at least one AE. None of the subjects discontinued the study due to AEs.

The incidence of subjects with AEs, fatal AEs, SAEs, treatment-related AEs and Grade ≥ 3 AEs did not substantially differ between treatment dose cohorts, and therefore the incidence of AEs, fatal AEs, SAEs, treatment-related AEs and Grade ≥ 3 AEs was not dose-related.

Table 12 Summary of Adverse Events, by Cohort (Safety Population; Dose-Finding Study, EudraCT No. 2012-001353-19)

	Treatment Group			
	DL1 (N=3)	DL2 (N=3)	DL2bis (N=7)	DL3 (N=3)
Number of deaths, N (%)	3 (100.0%)	1 (33.3%)	2 (28.6%)	0
AEs, N (%)	3 (100.0%), 70	3 (100.0%), 55	7 (100.0%), 146	3 (100.0%), 108
Deaths, N (%)	3 (100.0%)	1 (33.3%)	2 (28.6%)	0
SAEs, N (%)	1 (33.3%), 2	2 (66.7%), 3	2 (28.6%), 3	2 (66.7%), 4
Grade ≥ 3 AEs, N (%)	3 (100.0%), 22	3 (100.0%), 9	7 (100.0%), 22	3 (100.0%), 33
Treatment-related AEs, N (%)	0	0	1 (14.3%), 6	0
AEs leading to treatment discontinuation, N (%)	0	0	0	0

Abbreviations: AE, adverse events; E, number of events; N, number of subjects; SAE, serious adverse event.

Source: Clinical study report Addendum1, Dose-finding study, EudraCT No. 2012 001353-19, Table 14.3.1.1

All adverse events

The most commonly involved SOCs (i.e. in at least 50% of subjects overall) are displayed in Table 13 and the most commonly reported AEs by preferred term (i.e. in at least 25% of subjects overall) are displayed in Table 14.

Table 13 Most Commonly Reported Adverse Events by System Organ Class and Cohort (Safety Population; Dose-Finding Study, EudraCT No. 2012-001353-19)

System Organ Class	Treatment Group			
	DL1 (N=3)	DL2 (N=3)	DL2bis (N=7)	DL3 (N=3)
	N (%) E	N (%) E	N (%) E	N (%) E
Blood and lymphatic system disorders	0	2 (66.7%) 2	5 (71.4%) 28	1 (33.3%) 1
Gastrointestinal disorders	2 (66.7%) 10	2 (66.7%) 4	6 (85.7%) 20	3 (100%) 13
General disorders and administration site conditions	3 (100%) 8	2 (66.7%) 5	6 (85.7%) 15	2 (66.7%) 8
Infections and infestations	3 (100%) 11	2 (66.7%) 19	7 (100.0%) 17	3 (100%) 25
Investigations	3 (100%) 6	1 (33.3%) 2	4 (57.1%) 15	2 (66.7%) 14
Musculoskeletal of connective tissue disorders	2 (66.7%) 2	1 (33.3%) 1	3 (42.9%) 7	2 (66.7%) 12
Nervous system disorders	2 (66.7%) 4	1 (33.3%) 1	4 (57.1%) 4	1 (33.3%) 1
Skin and subcutaneous tissue disorders	3 (100%) 16	1 (33.3%) 1	5 (71.4%) 14	2 (66.7%) 18

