8.3.7 Safety Analyses

For each study treatment, numbers of AEs and incidence rates will be tabulated by MedDRA system organ class and preferred term. An event that occurred one or more times on the date of, or subsequent to, randomization will contribute one observation to the numerator of the incidence rate. The denominator of the rate will comprise all randomized subjects exposed to the study treatment. If the intensity or seriousness of the AE changes, then the overall intensity or seriousness will be the maximum intensity or seriousness of the multiple occurrences.

Serious adverse events, AEs leading to death and AEs leading to withdrawal of subjects will be tabulated for each treatment group. Commonly occurring AEs, i.e. those which occur in 5% or more of the subjects in either treatment group, will be summarized using descriptive statistics.

Descriptive statistics will be used to present physical examination results, weight, BMI, vital signs measurements; clinical laboratory test results; and ECG results – for both raw values and change from baseline. Shift tables will be presented for selected tests.

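### Section 8.3.7 relates neither AE incidence nor AE counts to time at risk, and incidence is insensitive for near-ceiling categories such as infections

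*Combined protocol and SAP*

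**What the plan says.** Section 3.1.3 makes comparing the safety and tolerability of the two arms an objective. The synopsis says that AEs "will be analyzed in terms of descriptive statistics and qualitative analysis".

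Section 8.3.7 gives the method: "For each study treatment, numbers of AEs and incidence rates will be tabulated by MedDRA system organ class and preferred term". For the incidence rate, "An event that occurred one or more times on the date of, or subsequent to, randomization will contribute one observation to the numerator", and "The denominator of the rate will comprise all randomized subjects exposed to the study treatment". SAEs, AEs leading to death and AEs leading to withdrawal are tabulated separately. The section mentions no person-time, rate ratio or interval.

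Section 6.2.1 records AEs from consent to Study Day 58 or 30 days after the last dose of study treatment, whichever is later. Section 5.9 lets BEGEDINA responders who flare after Day 28 and before Day 90 repeat the whole 28-day course. Conventional-arm subjects may continue or restart their therapy as the investigator judges.

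In the background, Section 2.1.2.2.2 reports "All subjects in all dose cohorts reported at least one AE" and concludes that AE incidences "did not substantially differ between treatment dose cohorts, and therefore the incidence of AEs, fatal AEs, SAEs, treatment-related AEs and Grade" ≥3 AEs were not linked to dose.

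**The concern.** A proportion of subjects with at least one event cannot rise much once it is close to 100%. If one arm had many more infections per subject, the incidence column for that system organ class would hardly move. Sections 2.1.1.1.2 and 2.3 name infection as a main source of morbidity and mortality in this disease, so this category matters to the comparative safety objective.

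The column of raw event numbers would move, but it mixes how often events occur with how long subjects are observed. The length of observation depends on the last dose, which need not fall at the same time in the two arms. A reader of the final tables would have one measure that is insensitive and one that is unadjusted, with no estimate of the difference between arms or its precision.

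**Working it through.** **Inputs.** Infections and infestations: pilot 12/13 subjects, 55 events (Table 5); dose-finding 3, 2, 7 and 3 subjects with 11, 19, 17 and 25 events (Table 13). Arm size is 92 (Section 8.1). The plan states no power for any AE comparison, so there is no such figure to reproduce. The arm size itself is plausible: the usual two-proportion formula for 50% vs 30% gives 93.

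**How near the ceiling.** (12 + 3 + 2 + 7 + 3)/29 = 27/29 = 93.1% (exact 95% CI 77% to 99%). Events: 55 + 72 = 127, or 127/29 = 4.4 per subject. Grade ≥3 AEs were 100% in all four dose-finding cohorts (Table 12).

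**Illustration of sensitivity.** Assume negative binomial counts with mean m and dispersion k, with k solved from 1 − (1 + km)^(−1/k) = baseline incidence. A rate ratio of 1.5 gives incidence 1 − (1 + 1.5km)^(−1/k). Incidence power is exact for a chi-square test; rate power uses SE(log RR) = √[(1/m + 1/(1.5m) + 2k)/92]. Both are two-sided 5%.

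| Baseline incidence | m | k | Incidence at 1.5× | Power, incidence | Power, rate |
|---|---|---|---|---|---|
| 93% | 3 | 0.08 | 97.8% | 31% | 99% |
| 93% | 4 | 0.28 | 97.0% | 20% | 97% |
| 93% | 5 | 0.43 | 96.5% | 16% | 95% |
| 77% | 3 | 0.88 | 83.8% | 21% | 73% |
| 77% | 4 | 1.19 | 82.8% | 16% | 64% |
| 77% | 5 | 1.43 | 82.2% | 14% | 59% |

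**Away from the ceiling.** CMV infection was 8/13 in the pilot and 7/16 in dose-finding, together 15/29 = 52%. With Poisson counts, a 1.5-fold rate gives 1 − (1 − 0.517)^1.5 = 66%, and power is about 53%. The limit there is sample size, not saturation.

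**Time at risk: treatment.** A flare on Day 89 puts the last dose of a repeated course at 89 + 27 = Day 116, and recording would then run to 116 + 30 = Day 146, against Day 58 for a subject who takes only the initial course. This assumes that the repeat course counts as study treatment. The conventional-arm window depends on the agent and on any restart, so the direction of the imbalance cannot be known in advance.

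**Time at risk: mortality.** Take constant hazards from the planned 50% and 30% by Day 180: h = −ln(0.5)/180 = 0.00385 and −ln(0.7)/180 = 0.00198 per day. Mean time at risk to Day 58 is (1 − e^(−58h))/h = 52.0 and 54.8 days, a difference of about 5%.

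**Background tables (DL1, DL2, DL2bis, DL3).** Any AE and Grade ≥3 AE are 100% throughout. Deaths are 100, 33, 29 and 0%; SAEs 33, 67, 29 and 67%; treatment-related AEs 0, 0, 14 and 0%. Grade ≥3 events per subject are 22/3 = 7.3, 9/3 = 3.0, 22/7 = 3.1 and 33/3 = 11.0. Person-days to death or Day 180, from Table 11, are 3 × 54 = 162, 24 + 360 = 384, 17 + 116 + 900 = 1,033 and 540. Grade ≥3 events per 100 person-days are then 13.6, 2.3, 2.1 and 6.1; infections are 6.8, 4.9, 1.6 and 4.6. Even deaths of 3/3 vs 0/3 give a Fisher p of 0.10.

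**The case against.** The strongest reply is that the plan does not rely on incidence alone. Event numbers are tabulated beside it by system organ class and preferred term, and with 92 per arm a large excess of infections would be visible there. That stands: a reader might infer that the trial could not see such an excess, and the documents do not support that. What the counts lack is adjustment for observation time and a measure of precision.

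It can also be said that no AE test is planned, so power figures describe an analysis nobody will run. This too is right; they only show how little the incidence column responds. The 93% comes from BEGEDINA subjects followed for 180 days or a year, so incidence in a window of about 58 days may be lower. The 77% rows show that the advantage of a rate comparison shrinks but remains.

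A reader might infer from the planned 50% vs 30% mortality that follow-up differs greatly by arm. Within 58 days it does not; the 5% gap is minor, and treatment-driven windows are the better reason for adjustment.

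Other parts of the plan cover some of the harm. Fatal infections without prior relapse enter TRM, all deaths enter OS, SAEs are tabulated separately, and the DSMB sees unblinded safety data. Section 8.0 also leaves further detail to the SAP, so a rate analysis could be specified outside the text available. Non-fatal recurrent infections remain without an adjusted comparison in Section 8.3.7.

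**Conclusion.** The point holds for AE categories near the ceiling and for comparisons in which observation time may differ by arm. For infections at 93% incidence, a 1.5-fold rate has 16-31% power on incidence and 95-99% on rates; at 77% it is about 14-21% against 59-73%. These figures assume that control-arm infections resemble the earlier BEGEDINA data, that counts are negative binomial with mean 3 to 5, and that arms have 92 subjects. They do not extend to preferred terms such as CMV.

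The background sentence is a lesser matter. Only two of its five measures are at 100%; for deaths, SAEs and treatment-related AEs the weakness is cohorts of 3 to 7. A reader might infer from 11.0 Grade ≥3 events per subject at DL3 that a dose effect was hidden. The documents do not support that: per person-day, DL1 is highest, and even that calculation is illustrative because the AE window of the earlier study is not given. The tables show neither a dose relation nor its absence.

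**What to change.** In Section 8.3.7 or the SAP, keep the existing tables. For infections (all and Grade ≥3) and for all Grade ≥3 AEs, add the event rate per subject-month at risk by arm, with time at risk ending at death, withdrawal or the end of AE recording. Give a rate ratio and two-sided 95% CI from a negative binomial or robust Poisson model stratified by baseline GvHD grade, labelled descriptive. Grade ≥3 infections were not at ceiling in the pilot (7/13, Table 7); they are included for the time-at-risk reason.

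In Section 2.1.2.2.2, replace the statements that toxicity was unrelated to dose with one saying that two measures were at ceiling and the cohorts were too small to judge the others.

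The cost is some SAP wording and a few tables. Section 6.2.1.2 already has each event recorded separately, so no new data are needed. The small downside is that a rule is needed for counting distinct infection episodes consistently.

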Most of the concentration levels of HAMA were not quantifiable based on the ELISA method, i.e. were below the limit of quantitation (3 ng/mL). Two subjects in the DL1 cohort, 3 in the DL2bis cohort and 3 in the DL3 cohort developed HAMA; no subject in the DL2 cohort developed HAMA. There was no evidence of correlation between serum concentrations of BEGEDINA and the possibility of developing HAMA.

There was no evidence of any correlation between the administered dose and concentrations of BEGEDINA with HAMA formation, and therefore, an influence of the antibody formation on the clearance on BEGEDINA can be excluded.

Pharmacodynamic assessments

The level of circulating lymphocytes CD3+/ CD26+ bound to BEGEDINA is the PD surrogate endpoint recommended by the Committee for Medicinal Products for Human Use (CHMP).

[figure not shown]
BEGEDINA-positive cell count (for counting lymphocytes CD26+ and CD3+) was performed using flow cytometry and staining with anti-mouse IgG within Day +5 of BEGEDINA treatment.

Dose change was scheduled as follows:

- In case of a maximum % BEGEDINA-positive cells on Day +5 of treatment $\geq 80\%$ at the first dose level (2 mg/m^2), 3 additional subjects were to be treated on the same dose;
- In case of a maximum % BEGEDINA-positive cells $< 80\%$ at the first dose level \rightarrow Second dose level: 3 subjects had to receive 3 mg/m^2 for 5 consecutive days;
- In case of a maximum % BEGEDINA-positive cells $\geq 80\%$ at the second dose, 3 additional subjects were to be treated on the same dose;
- In case of a maximum % BEGEDINA-positive cells $< 80\%$ at the second dose level \rightarrow Third dose level: 3 subjects had to receive 4.5 mg/m^2 for 5 consecutive days;
- In case of 6 subjects treated at the same dose level:
 - a. In case of a maximum % BEGEDINA-positive cells $< 80\%$, subjects had to be escalated to superior dose level
 - b. In case of a maximum % BEGEDINA-positive cells $\geq 80\%$, the dose level represented the MED level.

[figure not shown]
The concentration of BEGEDINA vs the respective levels of CD26/CD3/ μL is presented in Figure 4 and concentration of BEGEDINA vs the respective values of % binding to target CD26 (CD26 + / CD3 + / + Ig2B%) is shown in Figure 5. There was a wide inter-individual variability.

Figure 4 BEGEDINA Concentration vs Respective Levels of CD26/CD3/ μ L

(Dose-Finding Study, EudraCT No. 2012 001353-19)

2.1.3 Conventional Treatments for Graft-versus Host Disease

There are no approved second-line treatments for this group of subjects, although many have been investigated, as discussed in Section 2.1.1.1.2. However, guidelines for treatment have been published by the American Society of Blood and Marrow Transplantation (ASBMT) ([Martin et al., 2012](#)) and by the Working Group of the European Group for Blood and Marrow Transplantation and the European LeukemiaNet (EBMT-ELN) ([Ruutu et al., 2014](#)).

2.2 Rationale

Currently, there are no approved regimens for second-line therapy in subjects with acute GvHD who develop steroid-resistant disease. Survival in this group of subjects is poor and new treatment options are urgently needed.

Any clinically relevant result in this population would be of significant benefit as it would offer a clinically relevant advantage for steroid-resistant acute GvHD subjects.

BEGEDINA binding to CD26 antigen on T cells is able to inhibit activation, expansion and migration of T-cell population that plays a major role in GvHD development.

The rationale for the choice of endpoints is discussed in Section 4.3.3.

2.3 Risk Assessment

Steroid-resistant acute GvHD is associated with a high rate of morbidity and mortality, primarily from infections and/or multi-organ failure. Currently, there are no approved second-line regimens for treating subjects who develop steroid-resistant acute GvHD and those second-line therapies that are administered are largely unsatisfactory in terms of efficacy. For 30% of subjects, survival is no more than 1 year (Qian et al., 2013).

Any clinically relevant result in this population would be of significant benefit as it would offer a clinically relevant advantage for steroid-resistant acute GvHD patients.

The dose-finding study confirmed that BEGEDINA binds to circulating CD26+ T lymphocytes in patients with steroid-resistant acute GvHD. The efficacy endpoint was overall response (OR), which included patients with CR or PR to the BEGEDINA treatment (resolution of all signs of GvHD or improvement in grading of GvHD). Furthermore, the transplant mortality rate represents another efficacy endpoint to confirm the survival benefit.

The response rate on Study Day 28 for adults given BEGEDINA at the recommended schedule (3 mg/m² on Days +1, +2, +3, +4, and +5 and then on Days +10, +14, +17, +21, +24, and +28, considering Day +1 as the first day of treatment with BEGEDINA) was 85.7% and TRM at Day 180 was 28.6%.

Thus, if the efficacy of BEGEDINA can be confirmed in this study, it may provide benefit to this group of subjects in whom no satisfactory treatment options are available.

In clinical studies conducted to date, BEGEDINA has shown a good safety and tolerability profile; there was no evidence that there was an increased risk of toxicity at the higher doses.

This study will be performed in compliance with the protocol, ICH Good Clinical Practice (GCP) and applicable regulatory requirements, including the 2001/20/CE European Directive and the US FDA directive 21 CFR 314.126 - Adequate and well-controlled studies.

3.0 STUDY OBJECTIVES

3.1 Primary Objective

The primary objective of the study is to determine the efficacy of BEGEDINA versus conventional therapy in the treatment of subjects with steroid-resistant acute GvHD subjects in terms of OR at 28 days and TRM up to 180 days.

3.1.1 Secondary Objectives: Efficacy

The key secondary objective is to compare BEGEDINA and conventional therapy with respect to OS up to 180 days.

The other secondary efficacy objectives are to compare BEGEDINA and conventional therapy with respect to

- Change from baseline in stages of GvHD by target organ
- Incidence of chronic GvHD up to 180 days
- Cumulative steroid dose
- Incidence of Relapse and Relapse-Related Mortality
- Change from baseline in Karnofsky Performance Status

3.1.2 Secondary Objectives: Pharmacokinetic (PK)

The PK objective for this study is to characterize the PK of BEGEDINA in subjects with Grades II-IV acute GvHD who have failed to respond to steroid treatment.

3.1.3 Secondary Objectives: Safety

The secondary safety objectives are:

- To compare the safety and tolerability of BEGEDINA and conventional therapy.
- To gather additional information on the safety of BEGEDINA in subjects with Grades II-IV acute GvHD, who have failed to respond to steroid treatment.
- To evaluate the immunogenicity of BEGEDINA.
- To evaluate the effect of BEGEDINA on glucose metabolism.
- To compare the incidence of second malignancies at the end of the follow-up between BEGEDINA and conventional therapy.

